- a) At the end of the 12 weeks, the interventional arm will reach a clinically meaningful change in walking ability, as compared to controls, measured by a change in the 6-MWT at twelve-week, and 12 months; the minimal clinically important difference (MCID) is defined as +12m (7).

- b) At the end of the 12 weeks, $\geq 15\%$ interventional treatment arm participants will give up smoking or have significantly reduced their daily smoking compared to less than $\leq 10\%$ in the control arm.
- c) At the end of the 12 weeks, $\geq 50\%$ of interventional treatment arm participants will improve their medication adherence from pre- until post-intervention as compared to $< 30\%$ in the control arm.
- d) Healthcare cost will be reduced at 12 month follow-up in the intervention arm.

III. METHODOLOGY

We will implement a randomized controlled study of a 12-week lifestyle intervention for patients with peripheral arterial disease, delivered via the digital platform Sidekick Health. Participants will be recruited and randomized in a 1:1 manner to the digitally delivered intervention + standard of care or standard of care only. The standard of care group will receive an information leaflet on important lifestyle factors for PAD and smoking cessation and medical adherence will be encouraged by the health care provider. The interventional arm will receive a digital program delivered to their mobile phone alongside standard of care. Replicating a real-life scenario a personalized approach will be applied in the interventional arm, especially regarding smokers. Therefore, two pathways are possible in the interventional arm in this trial, one for smokers who want assistance in smoking cessation (PAD-SC) and another for non-smokers or those who smoke and do not desire to quit (PAD-Reg). Patients will be followed up at 12 weeks. We aim to do a separate follow-up at twelve months. The primary outcome will be a change in pain-free and maximal walking ability, measured by the 6-minute walking test. Secondary outcomes will include smoking status change (in PAD-SC group as compared to the control arm), medication adherence and lifestyle changes (increased physical activity, changes in self-assessed stress/energy/sleep quality levels), health-related quality of life, and a reduced need for hospitalization or revascularization due to PAD at 12 months of follow up.

Subject selection

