Individuals willing to participate and who provide written informed consent to the study will be further assessed and screened based on the inclusion and exclusion criteria presented in Table 1.

Table 1. Participant Criteria

Inclusion	Exclusion
Adults with confirmed PAD referred to a vascular surgery unit for evaluation and treatment, currently on best medical treatment and own/have access to a mobile smartphone	Critical limb ischemia, prior amputation, or other diseases/impairment that limit the walking ability and the 6-minute walk test's proper conduct
Stable PAD disease and limb symptoms during the last 3 months.	Cognitive impairment
PAD is the activity-limiting disease	Prior revascularization less than one year ago
Abnormal resting ankle-brachial index (≤ 0.90), falsely elevated above 1.3 or a 30% post-exercise ABI reduction.	A planned revascularization procedure during the upcoming 12 months (known at baseline)

Subject enrollment

Patients will be recruited by a clinic nurse or a medical doctor at participating centers (via telephone or during a scheduled in-person visit). Once agreed to participate and after signing informed consent, then the inclusion and exclusion criteria will be explored. Patients failing the screening process (do not meet the inclusion/exclusion criteria) may not participate in this study. Reasons for screen failure will be documented, but no other data will be collected. Participants who meet the criteria will be randomized to intervention or usual care in a 1:1 manner.

Based on a G*power analysis, the total number of patients in the two groups (intervention and control) will be 134, 67 in the intervention group and 67 in the control group, with an anticipated effect size of $f = 0.15$, $\alpha = 0.05$, power = 0.80 and correlations between time points (baseline and final timepoint) estimated at $r=0.25$. Foreseeing an attrition rate of 15%, we aim to recruit 155 patients to the trial.

Study procedures

All participants:

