Analyses will be performed according to the intention-to-treat principle and per-protocol analyses. Baseline characteristics and raw score questionnaire outcomes will be summarized as mean and SD for continuous measures and absolute numbers and percentages in each group. Changes in each outcome between baseline, post-intervention, and later a 12-month follow-up will be compared between and within the groups using t-tests or non-parametric statistical tests as appropriate. For the between-group differences, 95% Confidence Intervals will be reported. Correlations will be run to explore relationships between variables. For the primary outcome analyses, Ancovas or Mixed Anovas (repeated measures anovas) will be used, correcting for covariates that are significantly different between groups. The size of the change in HRQoL will be related to minimal important change values for the VascuQoL-6. It will be further assessed through effect size calculations (effect size=the difference in mean values between baseline and follow-up, divided by the SD at baseline). Cohen's criteria for interpreting effect sizes will be applied (small, 0.2–0.5; moderate, 0.5–0.8 and large, over 0.8). The a priori level for statistical significance will be set at a 2-sided $P < .05$.

V. RISKS AND DISCOMFORTS

We expect minimal to no risks and discomforts to be associated with this study. The lifestyle/behavioral change program is guideline-compliant for PAD patients and has

been reviewed by several medical doctors, behavioral scientists, and specialists in vascular surgery. Psychosocial risks will be minimal as well.

VI. POTENTIAL BENEFITS

Potential Benefits to Participating Individuals

The hope is that the intervention will increase participants' walking ability, reducing IC symptoms and prevent revascularization, empower participants to change their lifestyle and smoking patterns for the better, or that they will quit smoking altogether. Further, this intervention may also improve other patient-reported outcomes (e.g., reduce stress, improve sleep) without causing significant harm. Although the expected benefits are limited for patients that are allocated to usual care in the study, the enhanced follow-up at 12 weeks and 12 months may allow for a more careful evaluation and subsequent treatment of their condition following the end of study.

Potential Benefits to Society

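### Minor: at the stated 15% attrition, 155 recruits leave about 132 patients, not the planned 134; exact inflation gives 158, and 155 covers only 13.5% attrition

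*Combined protocol and SAP*

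**What the plan says.** Section III, Subject enrollment, reports a G*Power calculation with effect size f = 0.15, alpha 0.05, power 0.80 and a correlation of 0.25 between baseline and the final time point. From this, "the total number of patients in the two groups (intervention and control) will be 134", made up of "67 in the intervention group and 67 in the control group". The next sentence gives the recruitment target: "Foreseeing an attrition rate of 15%, we aim to recruit 155 patients to the trial". Allocation is 1:1. The paragraph does not say how 155 was derived from 134, and it does not name the G*Power test.

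Section IV, Statistical Methods, leaves the primary model open between two forms: "For the primary outcome analyses, Ancovas or Mixed Anovas (repeated measures anovas) will be used". It calls for intention-to-treat and per-protocol analyses but names no method for missing outcomes.

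**The concern.** An attrition allowance exists so that the number required by the power calculation is still there at the end. Attrition is a share of those recruited, so the required number is divided by one minus the attrition rate. The stated target looks as if the required number had been multiplied by one plus the rate, which always gives too few.

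The stakes are low. The recruitment target falls short of the plan's own sample size at the plan's own attrition rate, and anyone checking the paragraph will find that 15%, 155 and 134 do not agree. If the paragraph is reused in the trial report, the mismatch goes with it. The loss of power is under one percentage point.

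**Working it through.** **Inputs.** All are from section III, Subject enrollment: required total 134 (67 per arm), attrition 15%, recruitment target 155, allocation 1:1, f = 0.15, alpha = 0.05, power = 0.80, r = 0.25.

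**1. Reproduce 134.** The test is not named, so it is inferred. Take a repeated-measures ANOVA with 2 groups and 2 time points, testing the group-by-time interaction:

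- Noncentrality: lambda = N × 2 × f² / (1 − r) = 134 × 2 × 0.0225 / 0.75 = 8.04
- Degrees of freedom: 1 and N − 2 = 132
- Power: 0.8037

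134 is the smallest even total that reaches 0.80, so the plan's figure is reproduced. The within-subject time test has the same lambda and degrees of freedom and also returns 134. Other candidates do not: the between-group repeated-measures test needs 220, the interaction with three time points needs 110, and a one-way ANCOVA with one covariate (f on the residual SD) needs 352.

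**2. Reproduce 155.** 134 × 1.15 = 154.1, rounded up to 155. This is the likely route, but it is an inference. The mismatch in step 3 does not depend on it.

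**3. Apply 15% attrition to 155.**

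- Total: 155 × 0.85 = 131.75, about 132
- Per arm, if 155 splits 77/78: 77 × 0.85 = 65.45 and 78 × 0.85 = 66.30, both below 67

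**4. Correct inflation.** 134 / 0.85 = 157.6, so 158, or 79 per arm. Check: 79 × 0.85 = 67.15 per arm.

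**5. Attrition that 155 tolerates.** (155 − 134) / 155 = 21 / 155 = 13.5%.

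**6. Effect on power**, for either test that returns 134:

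| Completers | lambda | Power |
|---|---|---|
| 134 | 8.04 | 0.804 |
| 133 | 7.98 | 0.801 |
| 132 | 7.92 | 0.798 |

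**7. Chance of reaching 134.** Assume each patient independently has a 15% chance of loss. The number of completers is then binomial, and the chance of at least 134 is 36% with 155 recruits and 58% with 158.

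**The case against.** The strongest objection is that nothing turns on this. The 15% is a forecast and 155 is an aim. Under the binomial assumption the SD of the number of completers at 155 recruits is √(155 × 0.85 × 0.15) ≈ 4.4, so a gap of about 2 is less than half an SD. The total of 134 is itself rounded up for equal arms, and 133 would already give 0.801. Averaged over the same binomial distribution, power is 0.797 with 155 recruits and 0.804 with 158. The contrast of 36% with 58% therefore looks larger than its consequence: it concerns hitting an exact count, and 158 also misses that count 42% of the time. All of this stands, and it is why the point is minor.

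A second objection is that the paragraph never calls the 134 completers, and that 15% could be meant as an addition to 134. The first part is literally true. But 134 is the output of the power calculation, and an allowance for attrition has no other purpose than to protect that number. An attrition rate is a fraction of those who enter, so the add-on reading does not rescue the sentence.

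Third, the 77/78 split is not guaranteed, because randomisation is stratified by site and smoking status. That is fair. The per-arm figures are illustrative, and the total of 131.75 does not depend on them.

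Finally, ANCOVA is also permitted and could lose even less. For a 0.6 SD difference at r = 0.25, power would be 94.5% with 134 and 94.2% with 132. This bears on the consequence, not on the arithmetic. It is also not a statement of the trial's actual power, since the plan does not say that f = 0.15 means 0.6 SD.

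**Conclusion.** The concern holds, as a minor point. With 134 read as the number to be analysed and 15% as a share of recruits, the three stated figures are incompatible: 155 delivers about 132, and 134 needs 158. The shortfall is about 2 completers or 3 recruits (3 / 158 = 1.9%). Power falls from 0.804 to 0.798, conditional on the inferred two-group, two-time-point test. Nothing elsewhere in the document corrects it.

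The conclusion does not extend further. The figure of 134 reproduces and is not challenged. Nothing is claimed about power for the 12 m minimal clinically important difference in hypothesis (a), because the document gives no SD for the walking test.

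**What to change.** Keep 155 and reword the sentence in one of two ways:

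- State that 155 patients will be recruited and that 15% attrition would leave about 132 completers, with power of about 0.798 for the test used to obtain 134.
- State that 155 patients will be recruited, which allows for 13.5% attrition while retaining 134 completers.

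Either is a one-sentence edit with no extra patients. The first keeps the 15% forecast; the second changes it to what 155 can bear. If both 15% and 134 are to be kept, the target becomes 158 (79 per arm), at a cost of 3 more recruits.

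As an optional clarification in the same paragraph, not a correction: name the G*Power test, give the assumed SD of the walking distance and the target difference in metres, and say that the between-group 95% confidence interval will be read against 12 m. Naming the test matters because f = 0.15 is a 0.6 SD between-arm difference in change under the interaction test, but a 0.3 SD pre-post change under the time test. Any power statement in SD units should name the analysis and the correlation it assumes.

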Clinical Study Protocol

ClinicalTrials.gov entry no.	NCT05029739
Version number	1.0
Date of ethical approval	July 13, 2021

A Mobile Intervention for Patients with Peripheral Artery Disease (I-PAD): a Prospective Randomized Open Blinded End-point (PROBE) study

I. BACKGROUND AND SIGNIFICANCE

Peripheral artery disease (PAD) is a highly prevalent atherosclerotic syndrome with an estimated global population burden of ~200 million people (1). Patients with PAD are at heightened risk for adverse cardiovascular and limb events and impaired quality of life (2). Cigarette smoking is the most important modifiable risk factor for PAD. Patients with PAD who smoke have higher disease progression rates, greater risk of complications, poor post-procedural outcomes, compromised functional status, and increased hospitalizations, accounting for a higher patient and societal burden (3).

A significant goal of PAD treatment includes risk factor modification and prevention of cardiovascular events. Guideline directed therapy includes cardioprotective pharmacotherapies (i.e., antiplatelet therapy; statins; and blood pressure control, preferably with angiotensin-converting enzyme inhibitors (ACE-I) or angiotensin receptor blockers (ARBs)), and lifestyle modification (i.e., changes in diet, physical activity, and smoking cessation) (2). Nevertheless, adherence to pharmacologic and lifestyle recommendations in PAD is uncertain (4). Effective non-pharmacologic therapies for PAD also exist, including smoking cessation, exercise support, and diet counseling (5). However, limited data is available on mobile applications offering digitally delivered lifestyle change support, including a structured exercise program and smoking cessation support (6). This study aims to digitally provide lifestyle change support, including a structured and PAD-focused lifestyle program and smoking cessation support via a mobile platform (Sidekick Health) with the primary aim to increase patients' walking ability and secondary aims to reduce smoking and improve medication adherence.

II. SPECIFIC AIM

The specific aim is to determine whether a 12-week digitally delivered behavior change intervention for patients with peripheral artery disease increases walking ability, reduces smoking, improves quality of life and improves medication adherence. A follow-up visit after 12 months will be planned, to assess longer term effect on outcomes and healthcare cost.

Hypotheses

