Vascular Quality of Life Questionnaire (VascuQoL-6)	Yes	Yes	Yes
Morisky Medication Adherence Scale (MMAS-8)	Yes	Yes	Yes
Quality of life questionnaire – assessed by EQ5D5L	Yes	Yes	Yes
Assessment of health literacy (HLS-EU-Q16 Swedish version)	Yes	-	-
Carbon Monoxide breath monitor (smokers only)	Yes	Yes	Yes
Smoking Readiness to Quit Ladder (smokers only)	Yes	Yes	Yes
Daily frequency of cigarettes smoked (smokers only)	Yes	Yes	Yes
Intervention arm only			
In-app 6-minute walking test	Yes	Yes	Yes
Free-living physical activity (measured as total step count per day)	Yes (week 1)	Yes	-
In-app metrics (e.g. stress/sleep/energy level self-assessment)	Yes (week 1)	Yes	-

Measures – copies of questionnaires will be included in this protocol when finalized in section VIII below (Study Questionnaires)

IV. BIOSTATISTICAL ANALYSIS

Variables to be collected

Participants' demographic and background information, including age, gender, height, weight (and BMI), tobacco use, co-morbid medical or psychiatric conditions, and information on any current medical therapy they may or may not be receiving will be collected. All participants should be on the best medical PAD treatment available for them, and the control arm will receive an information leaflet about relevant lifestyle modifications for PAD. A 6MWT, questionnaires, and validated survey instruments (10) will be administered both pre-and post-intervention and 12 months from the start of the intervention.

Primary Outcomes (Intervention KPIs)

As far as possible, evaluation of endpoints will be done by evaluators blinded to the treatment assignment (PROBE design).

- Walking Ability: Change in patients objectively measured walking ability (measured by the 6-Minute Walk Distance Test) from pre- to post-intervention and 12 months.

Secondary Outcomes

- Smoking status: Change in patients' daily smoking patterns from pre to post-intervention and at twelve months. This will be based on information from the patient, supported by read-outs from the carbon monoxide breath monitor at baseline, 12 weeks and one year.
- Medication adherence improvement.
- Lifestyle behavioral changes (measured in-app):
 - Changes in free living physical activity, measured as total step count per day (from baseline to week 12)
 - Changes in self assessed stress levels, measured on an ordinal scale from 0-10 (from baseline to week 12)
 - Changes in self assessed energy levels, measured on an ordinal scale from 0-10 (from baseline to week 12)

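### Smoking status rests on the patient's own report in an open trial: no rule lets a CO reading overturn a claimed quit, and the comparison named in Methodology is not between randomised groups.

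*Combined protocol and SAP*

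**What the plan says.** The title page describes a "Prospective Randomized Open Blinded End-point (PROBE) study", so patients know their allocation. Section IV, Primary Outcomes, adds: "As far as possible, evaluation of endpoints will be done by evaluators blinded to the treatment assignment (PROBE design".

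Hypothesis (b) in section II sets a 12-week target of at least 15% in the intervention arm against at most 10% in controls. Its success event is a composite: "interventional treatment arm participants will give up smoking or have significantly reduced their daily smoking". The plan sets no threshold for a significant reduction.

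Section IV, Secondary Outcomes, defines the measurement: "This will be based on information from the patient, supported by read-outs from the carbon monoxide breath monitor". The readings are planned at all three visits. Table 2 in section III lists the test as "Carbon Monoxide breath monitor (smokers only") without saying whether that means smokers at baseline or at the visit.

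Section III (Methodology) describes the smoking comparison as PAD-SC against the control arm. PAD-SC consists of intervention-arm smokers who want help to stop. Under Study procedures, that help is offered after the first week of the programme, so membership is settled after randomisation. Statistical Methods names both intention-to-treat and per-protocol analyses, without saying which applies to smoking.

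**The concern.** A blinded evaluator cannot mask what an unblinded patient says. App-arm smokers who accept the offer get a cessation pathway inside a gamified programme. Controls get advice and a leaflet, with no scheduled provider visit until week 12. It is plausible, though the documents do not measure it, that unsupported claims of success would be more common in the app arm.

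An objective check is scheduled, but the plan gives it no force. There is no cut-off, no rule for a claim that disagrees with the reading, and no rule for a missing reading. CO could be collected at every visit and never alter a classification, or be applied case by case once results are known.

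A second bias points the same way. Smokers who choose cessation support are likely to be more motivated than smokers in general, and the control arm has not been filtered in that way. At stake is a secondary outcome that appears in the specific aim and has its own numerical hypothesis.

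**Working it through.** **Does any text let CO decide?** Three places bear on this.
- The Secondary Outcomes text makes CO supportive of the patient's account.
- Table 2 schedules the test at baseline, after week 12 and at 12 months.
- Statistical Methods does not mention CO.

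None says when a reading overrides a report.

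**Who is tested?** The smokers-only label in Table 2 also sits on the readiness ladder and the daily cigarette count, each at all three visits. Rungs 9 and 10 of the ladder, printed in the questionnaire annex, are for people who have quit. Randomisation is stratified by smoking status, which is fixed at entry. Both facts favour baseline smokers as the intended meaning.

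**How many false claims matter?** The plan gives no sample size or power for smoking, so there is no planned figure to reproduce.

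Inputs:
- 67 evaluable patients per arm (Subject enrollment).
- 15% v 10%, a gap of 5 points (hypothesis b).
- Share of smokers: not in the documents. **Assumption:** 30% to 50%, so 67 × 0.30 = 20.1 and 67 × 0.50 = 33.5, taken as 20 and 33 per arm.

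Formula: shift in the app-arm rate = false claims / smokers per arm. The 5-point gap in people is 0.05 × 20 = 1.0 and 0.05 × 33 = 1.65.

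With equal true cessation in both arms, at or just under 10%, and no false claims among controls:

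| Smokers per arm | Control | App arm, true | False claims | App arm, observed | Shift | Fisher p |
|---|---|---|---|---|---|---|
| 20 | 2 (10.0%) | 2 | 1 | 3 (15.0%) | 5.0 points | 1.0 |
| 33 | 3 (9.1%) | 3 | 2 | 5 (15.2%) | 6.1 points | 0.71 |

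**As a rate.** Observed = 0.10 + 0.90 × q, where q is the share of continuing app-arm smokers who falsely claim success.
- q = 2% gives 0.118.
- q = 5% gives 0.145.
- q = 0.05/0.90 = 5.6% gives 0.150. This value is solved backwards from the target; it is not an estimate.

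**Wider assumption.** If 20% to 50% of 67 to 77 patients per arm smoke (13 to 38 smokers), 1 to 3 false claims take the app arm from no true effect to at least 15%. If every participant is counted, it takes 5. Across all these cases Fisher p is 0.30 to 1.0.

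**Against significance.** On the 13 to 38 range, 6 to 8 false claims would be needed for P < .05. The standard error of 15% v 10% is √[(0.15 × 0.85 + 0.10 × 0.90)/n]: 10.4 points for n = 20 and 8.1 points for n = 33. Both exceed the 5-point shift.

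**The case against.** **Quitters are tested.** A reader might infer from Table 2 that someone who reports having quit is no longer a smoker and escapes the breath test. The documents do not support that as the likely meaning. The ladder under the same label has rungs for quitters, and excluding quitters from the cigarette count would defeat the outcome. This objection stands, and what remains of the Table 2 point is a request to clarify the label.

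**A few claims do not make a result.** A reader might infer that one or two false claims could produce a positive finding. They could not: they move the point estimate, not the significance test. This also stands. However, the plan promises between-group differences with 95% confidence intervals, so a biased estimate would be reported whether or not it is significant.

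**The illustration is favourable to the concern.** It sets false claims among controls to zero, although controls also receive cessation advice and might over-report; that would shrink the gap. It also models cessation alone, whereas hypothesis (b) counts reduction too, so it does not reproduce that hypothesis. Both points are fair, and the figures should be read as scale only.

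**The outcome is secondary.** The primary outcome is a measured walk. That limits the weight of the point but does not answer it.

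**Counting missing CO as smoking can itself bias.** This is correct if missingness differs by arm; the plan expects 15% attrition overall. A sensitivity analysis is therefore needed.

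**Conclusion.** The point holds in a limited form. The firm gap is the absence of any rule by which CO changes a smoking classification in a trial open to patients. The PAD-SC versus control comparison is a further weakness, because one side is self-selected after randomisation. The Table 2 label needs only clarifying.

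On the assumed 20 to 33 smokers per arm, with no over-reporting in controls, one or two false quit claims shift cessation by about 5 points, equal to the hypothesised gap. The direction of bias is inferred from the design, not shown by data.

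A reader might also infer that CO would remove all reporting bias from hypothesis (b). It would not: reduced smoking rests on reported cigarette counts and stays unverified. This should be changed, but it does not threaten the primary outcome.

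**What to change.** 1. In Table 2, state that CO is measured in all participants recorded as smokers at baseline, in both arms, whatever they report at the visit.
2. Define cessation as self-reported abstinence plus CO below a cut-off fixed before the data are analysed. Count discordant readings as smoking. Count missing readings as smoking in the main analysis, with a sensitivity analysis under other assumptions.
3. Compare all baseline smokers by randomised arm. Replace the PAD-SC versus control comparison in section III with this.
4. Report self-reported reduction separately from cessation, with a stated threshold, and label it unverified.

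The cost is mostly wording. The monitor and all three visits are already planned, so at most a few extra breath readings follow. The downsides are somewhat lower quit rates in both arms and possible bias if missing CO differs by arm, which the sensitivity analysis addresses.

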After recruitment, measurements and data collections will occur at each clinic by a experienced clinic or research nurse, as shown in table 2 and further detailed under section VIII. Furthermore, a 6-minute walking test will be administered by a trained clinic nurse at baseline, after 12 weeks and for a separate follow-up at 12 months. The American Thoracic Society protocol for the 6-minute walking test, modified for patients with intermittent claudication (IC), will be used. The 6MWT has excellent test-retest reliability for patients with IC. (8, 9). A central computerized procedure will randomly assign participants to treatment arms, stratified for study site and smoking status.

Intervention:

Participants will be instructed to download the SKH mobile app, and they will receive an access code to activate the PAD lifestyle change program. After the first week of the program, participants who smoke will be offered to incorporate smoking cessation support into their PAD program. These changes are minor and not intended to divide the intervention group in two but instead personalize the experience. Personalization of the program is essential for engagement and to deliver the most meaningful impact on clinical outcomes. The program aims to empower positive lifestyle change by gamification, altruistic rewards, and engaging content with relevant tasks or missions to be completed. Beyond this, all patients in the interventional arm will also receive standard of care as defined below for the control arm.

Participants in the intervention group will also be asked to do a separate and virtually delivered 6-minute walking test to validate the digital in-app 6MWT.

Control:

All patients in the control arm will receive best medical treatment including start or optimization of secondary preventive pharmacotherapy, smoking cessation advise and advise on modifiable risk factors. The control arm will also receive an information leaflet about relevant lifestyle modifications for PAD. After baseline measurements and data collection, there will be no scheduled visits by a health care provider until week 12.

Table 2. Timing of Proposed Data Collection and Instruments Used

Data collection/Instruments	Baseline	Post-Intervention (after week 12)	12-month follow-up
All participants (intervention and control)			
Demographic and Clinical/Medical Baseline Information (e.g., tobacco use, other risk factors, and comorbidities)	Yes	Yes	Yes
6-Minute Walking Test	Yes	Yes	Yes

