 - Changes in self assessed sleep quality, measured on an ordinal scale from 0-10 (from baseline to week 12)

- Disease-specific health-related quality of life.
- Increased readiness to quit smoking.
- Comparing outcomes to health literacy.
- Comparing healthcare costs between groups. Following completion of the long-term follow-up at 12 months for all patients, a separate cost-effectiveness analysis will be undertaken, based on the prospectively collected EQ5D-5L data and accumulated costs per patient as registered in the participating hospital's cost-per-patient databases. Quality Adjusted Life Years (QALYs) and Incremental Cost-Effectiveness Ratio (ICER) will be the main analyzed endpoints.

[figure not shown]
Retention and Engagement

- Program uptake (number of app downloads, how many participants/potential quitters registered (including gender and age)
- Length of program participation
- Program usage patterns (how often do people visit, how many tasks are performed, which tasks (videos, daily tasks, other) are used/accessed, etc.)
- Pre/post assessment of medication therapy (as registered medication taken)

End of study

The formal trial completion is when the recruited patients have completed the 12-week intervention, but an extended follow-up at twelve months from study start will also be arranged.

IPAD STUDY DESIGN

Statistical Methods

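### The between-arm test for VascuQoL-6 uses unadjusted change scores; baseline-adjusted ANCOVA would be more precise at almost no cost

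*Combined protocol and SAP*

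**What the plan says.** Section IV, Statistical Methods, sets one general rule. Its subject is "Changes in each outcome between baseline, post-intervention, and later a 12-month follow-up". The method laid down is that these "will be compared between and within the groups using t-tests or non-parametric statistical tests as appropriate". It also promises 95% confidence intervals for between-group differences. Adjusted models appear once: "For the primary outcome analyses, Ancovas or Mixed Anovas (repeated measures anovas) will be used, correcting for covariates that are significantly different between groups". The primary outcome is the 6-minute walk test.

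The Secondary Outcomes list includes "Disease-specific health-related quality of life". The Statistical Methods tie this to VascuQoL-6 by reading the size of change against that instrument's minimal important change values. They add an effect size: the baseline-to-follow-up difference in means over the baseline SD. Neither is an adjusted comparison between arms.

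Table 2 has VascuQoL-6 collected in all participants at baseline, after week 12 and at 12 months. On allocation, Study procedures in section III state: "A central computerized procedure will randomly assign participants to treatment arms, stratified for study site and smoking status". No analysis is said to include those two factors.

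Section II makes quality of life part of the aim, which is whether the programme "increases walking ability, reduces smoking, improves quality of life and improves medication adherence".

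**The concern.** Subtracting the baseline score fixes its coefficient at 1. ANCOVA estimates the coefficient from the data, and with equal SDs at the two times it equals the correlation r, which is below 1. The change score therefore over-corrects for baseline and carries extra noise. Site and smoking status constrain the randomisation, but any variation they explain stays in the error term.

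At stake is the precision of the quality-of-life result. The interval is wider than the collected data allow, so a real benefit is more likely to be reported as inconclusive. The sample size is not stated to have been set for this outcome.

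**Working it through.** **Inputs from the documents.** Section III, Subject enrollment: 67 per arm, f = 0.15, α = 0.05, power 0.80, r = 0.25 between baseline and the final time point. Statistical Methods: two-sided testing. Not given: any correlation or SD for VascuQoL-6, or the number of sites.

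**Step 1. Reproduce the plan's sample size.** Repeated-measures ANOVA, group-by-time interaction, two groups and m = 2 times:

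λ = f² × N × m / (1 − r) = 0.0225 × 134 × 2 / 0.75 = 8.04, on 1 and 132 df.

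Power is 80.4% at N = 134 and 79.8% at N = 132, so 134 reproduces. With two time points this test is the same as a two-sample t-test on change. The implied difference in change is √(4 × 0.0225 × 2/0.75 × 2 × 0.75) = √0.36 = 0.6 SD.

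**Step 2. Compare the two methods with equal SDs.** In units of the outcome variance:

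- change score: 2(1 − r)
- baseline-adjusted: 1 − r²
- ratio: (1 − r²) / [2(1 − r)] = (1 + r)/2, which is below 1 for every r below 1
- narrowing of the interval: 1 − √[(1 + r)/2]

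Power is from the noncentral t with 67 per arm; ANCOVA loses one further df. For each r, the effect is the one that gives the change-score test 80% power.

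| r | Variance ratio | Interval narrower by | Effect (SD) | ANCOVA power |
|---|---|---|---|---|
| 0.25 | 0.625 | 21% | 0.597 | 94.3% |
| 0.5 | 0.75 | 13% | 0.488 | 89.9% |
| 0.7 | 0.85 | 8% | 0.378 | 86.0% |
| 0.9 | 0.95 | 3% | 0.218 | 82.0% |

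At the plan's own implied effect (0.6 SD, r = 0.25), power goes from 80.4% to 94.5%.

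**Step 3. Relax the equal-SD assumption.** Let the follow-up SD be k times the baseline SD. In units of the baseline variance, the change score has 1 + k² − 2rk and ANCOVA has k²(1 − r²). The difference is (1 − rk)², which is never negative, so apart from the df spent ANCOVA is not less precise for any k. The size does depend on k. With k = 1.2 (an assumption) and the same 80% benchmark:

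- r = 0.5: 1.08/1.24 = 0.871, ANCOVA power 85.1%
- r = 0.6: 0.9216/1.00 = 0.922, 83.1%
- r = 0.7: 0.7344/0.76 = 0.966, 81.3%
- r = 0.75: 0.63/0.64 = 0.984, 80.6%

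The gain there is about 1 to 5 points. With k below 1 it is larger than in Step 2.

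**Step 4. Chance baseline imbalance.** The SD of the baseline difference between arms is √(2/67) = 0.173 SD. With equal SDs, a difference of that size moves the change-score estimate by (1 − r) × 0.173, which is 0.13 SD at r = 0.25 and 0.09 SD at r = 0.5. Since 2(1 − r) = (1 − r²) + (1 − r)², the second term is exactly this sensitivity. It is the loss of Step 2 seen another way and must not be added to it.

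**Step 5. Stratification factors.** Any gain depends on how strongly site and smoking status predict VascuQoL-6. The documents do not say, so it cannot be sized.

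**The case against.** The strongest defence is that nothing here is invalid. In a randomised trial a two-sample test on change keeps its error rate, and its estimate is unbiased over randomisation. That stands. A reader might infer that the planned comparison is biased, or that baseline is ignored. The documents support neither, because the change score does use baseline, only inefficiently.

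Second, quality of life is in the aim but in none of hypotheses a to d, and the trial is not stated to be sized on it. That stands too, and it keeps the severity low.

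Third, r = 0.25 is the sample-size assumption and is not tied to VascuQoL-6. A reader might take the 14-point gain at that value (80% to 94%), or a minimum gain of 5 points, as established. Neither is. Step 2 gives about 2 points at r = 0.9, and Step 3 gives about 1 point at r = 0.7 to 0.75 with a 20% larger follow-up SD. The 80% benchmark is itself a construction, with a different effect at each r.

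Fourth, VascuQoL-6 is a bounded sum of six items scored 1 to 4, so allowing a non-parametric test is defensible. The plan promises confidence intervals for between-group differences in any case, and its comparison with minimal important change concerns change from baseline. The documents therefore do not support reading the rank-test option as an error, or as defeating that comparison.

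What the defence does not supply is an adjusted between-arm model for VascuQoL-6. Even stretching the primary-outcome sentence to cover it would not guarantee adjustment for baseline score, because that sentence admits only covariates that differ significantly between groups.

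**Conclusion.** The point holds as a matter of efficiency. The plan's only stated between-arm test for VascuQoL-6 is valid but less precise than a baseline-adjusted analysis of data it already collects.

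With equal SDs, 67 per arm and r from 0.25 to 0.9, the gain over an 80% change-score test runs from about 14 points of power down to 2, and the interval is 21% to 3% narrower. These figures rest on assumed correlations and SDs. The direction does not, but the gain can be close to nil if the follow-up SD is larger than the baseline SD and r is high. Low severity: a free improvement to a secondary analysis.

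**What to change.** For VascuQoL-6 at week 12, and separately at month 12, state that the main between-arm analysis is an ANCOVA of the follow-up total score on arm. Adjust for baseline VascuQoL-6, study site and smoking status, whether or not these differ significantly at baseline. Report the adjusted mean difference with its 95% confidence interval. A non-parametric test may stay as a sensitivity analysis.

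The cost is about one sentence in the Statistical Methods, using a method the plan already names for the walk test. It needs no extra data, visits or patients. The downside is a few degrees of freedom for site; the number of sites is not stated. As an illustration, spending six further df at 67 per arm changes the power figures in Step 2 by about 0.02 to 0.03 percentage points.
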